#### SPECT:

20. Specific Binding Ratio (SBR) in the striatum, putamen, and caudatus from baseline SPECT-scan to follow-up after 26 weeks of treatment, adjusted for baseline.

#### fMRI:

- 21. Blood oxygenation level-dependent (BOLD) percent signal change (contrast "alcohol vs. neutral cues") in the ventral striatum (nucleus accumbens), the putamen and the caudatus. Group (exanetide or placebo), session (baseline or follow-up scan), and patients vs healthy control-group.
- 22. Craving data acquired during fMRI scan. Group (exanetide or placebo), session (baseline or follow-up scan), category (alcohol or neutral stimuli) and patient vs healthy control-group.

### Analysis methods

All continuous outcomes, i.e., change in metabolic parameters, weight, body composition parameters, alcohol use, etc. will be analyzed using ANOVA from baseline to last observation endpoint. Categorical outcomes will be analyzed using chi-square analyses. As the study was conducted as a randomized trial, no covariates adjustment is in principle necessary to assess causal effects.

Edition: 1.0

26.05.20

Statistical Analysis Plan

EudraCT 2016-003343-11

We will use residual plots and qq-plots in combination with Wally plots to validate the normality assumptions of the residuals in the ANOVA models. If the distributional assumption about normality of the residuals does not hold then we will first see if a log-transform of the outcome will result in a model fit that does not appear to violate the assumptions of normality. If the log-transform still does not hold, our next step will be to consider if the lack of fit is caused by inflation, e.g. due to too many observations being zero. Should that be the case we will replace the standard ANOVA model with a zero-inflated gaussian mixture model for the analyses. Should none of these approaches work we will use quantile regression and model the median outcome instead.

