#### Randomization

The participants were randomised in two groups, exanetide or placebo. The randomisation was stratified in terms of age, sex, and baseline alcohol consumption i.e. the number of heavy drinking days in the last 30 days before inclusion measured by the TLFB-method (5-11, 12-17, 18-23, 24-30 days). For this stratified randomisation, the randomisation tool in REDCap was used. Patients, investigators, other caregivers performing assessments, and persons performing data analysis have been blinded from the time of randomisation and until the time of database unlock. To maintain the blinding, the participants were blindfolded and an un-blinded nurse prepared the injections in a separate room and gave the injection immediately after.

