#### Baseline Patient characteristics

List of baseline characteristics to be summarised:

- Sex
- Age mean
- Age group (+/- 40 years)
- Education (lower secondary school, upper secondary school, vocational education + short-cycle higher education, medium cycle higher education + higher education)
- Marital status (yes, no)
- Job-status (yes, no)
- Heavy days, mean
- Heavy days group (5-11, 12-17, 18-23, 24-30)
- Baseline AUDIT score, mean
- Baseline AUDIT group (15-19, 20-40)
- 0-days during the prior 30 days to inclusion, mean
- Total alcohol consumption during the prior 30 days to inclusion, mean
- ICD-10 number of diagnostic items (4,5,6)
- DSM-5 group (mild(2-3), moderate(4-5), severe(>6))

Baseline characteristics will be descriptively summarized in a table assessed by the intervention

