# Analysis

#### Outcome definitions

#### Primary endpoint

Percentage of heavy drinking days during the last 30 days, at follow-up after 26 weeks of treatment adjusted for baseline (percentage points (pp)). A heavy-drinking day is defined as a day with an excess intake of 60/48 grams (men/women) of alcohol per day. Data will be registered via the Timeline-Follow-Back-method (TLFB).

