# Secondary endpoints

- 1. Total alcohol consumption (gram/day) during the last 30 days, at follow up after 26 weeks of treatment adjusted for baseline. Data will be registered via the Timeline-Follow-Back-method (TLFB).
- 2. Percentage of days without any alcohol consumption during the last 30 days, at follow-up after 26 weeks of treatment adjusted for baseline (percentage points (pp)). Data will be registered via the Timeline-Follow-Back-method (TLFB).
- 3. Phosphatidylethanol (PEth) (ng/mL) at follow-up after 26 weeks of treatment, adjusted for baseline.
- 4. Penn Alcohol Craving Scale (PACS) score at follow-up after 26 weeks of treatment, adjusted for baseline.

Rigshospitalet

Statistical Analysis Plan

Edition: 1.0

EudraCT 2016-003343-11

- 5. Alcohol Use Disorders Identification Test (AUDIT) score at follow-up after 26 weeks of treatment, adjusted for baseline.
- 6. Screen for Cognitive Impairment in Psychiatry test (SCIP) score at follow-upafter 26 weeks of treatment, adjusted for baseline and week 4.
- 7. The liver parameter alanine aminotransferase (ALAT) (U/L) at follow up after 26 weeks of treatment, adjusted for baseline.
- 8. The liver parameter gamma-glutamyl transferase (GGT) (U/L) at follow up after 26 weeks of treatment, adjusted for baseline.
- 9. Mean cell volume (MCV) (fL) at follow up after 26 weeks of treatment, adjusted for baseline.
- 10. Short-Form Health Survey (SF-36) score at follow-up after 26 weeks of treatment, adjusted for baseline.
- 11. Symptom Checklist (SCL-92) score at follow-up after 26 weeks of treatment, adjusted for baseline.
- 12. Bodyweight (kg) at follow-up after 26 weeks of treatment, adjusted for baseline.
- 13. Blood pressure (mmHg) at follow-up after 26 weeks of treatment, adjusted for baseline.
- 14. Pulse (PR) at follow-up after 26 weeks of treatment, adjusted for baseline.
- 15. Waist circumference (cm) at follow-up after 26 weeks of treatment, adjusted for baseline.
- 16. Glycemic control parameters HbA1c (mmol/L) at follow-up after 26 weeks of treatment, adjusted for baseline.
- 17. Kidney function (urine albumin/creatinine ratio) at follow-up after 26 weeks of treatment, adjusted for baseline.
- 18. Drug Use Disorders Identification Test (DUDIT) score at follow-up after 26 weeks of treatment, adjusted for baseline.

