- 19. Percentage of heavy drinking days during the last 30 days, at the long term follow up 26 weeks after termination of intervention, adjusted for baseline and end of treatment (week 26) (percentage points (pp)).

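### Endpoints are defined as follow-up values adjusted for baseline, but the only named main model is an ANOVA of change without covariates, and the SAP does not reconcile the two

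*SAP*

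**What the plan says.** **Endpoint definitions.** The SAP, Primary endpoint, defines the outcome as "Percentage of heavy drinking days during the last 30 days, at follow-up after 26 weeks of treatment adjusted for baseline". Secondary items 1 to 19 follow the same pattern. Two of them adjust for two earlier values: item 6 (SCIP) is "adjusted for baseline and week 4", and item 19 (long-term heavy drinking days) is "adjusted for baseline and end of treatment (week 26".

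**Model.** Analysis methods covers all continuous outcomes, describes them as changes, and states that change in "alcohol use, etc. will be analyzed using ANOVA from baseline to last observation endpoint". It then adds: "As the study was conducted as a randomized trial, no covariates adjustment is in principle necessary to assess causal effects". The Additional analysis section calls the intention-to-treat comparison primary but names no model form.

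**Stratification.** Under Randomization: "The randomisation was stratified in terms of age, sex, and baseline alcohol consumption", the last in four bands of heavy drinking days. In the rest of the SAP, age and sex appear only in the baseline table, where the age split is listed as "Age group (+/- 40 years". The Randomization section gives no age cut.

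**The concern.** A follow-up value adjusted for baseline is ordinarily a regression (ANCOVA) in which the data set the weight given to baseline. An ANOVA of change fixes that weight at 1. The two coincide only if the slope of follow-up on baseline is 1 or the arms have identical baseline means. A statistician could follow the endpoint section, another the methods section, and they could report different primary p-values from the same locked data.

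The SAP does have a safeguard. Timing of final analysis locks the data and the SAP before the split into groups A and B, and keeps the treatment labels hidden. That prevents a choice steered by the known direction of benefit. It does not prevent one steered by the size of a two-sided p-value. Item 19 lacks even this protection, because the long-term data are to be analysed unblinded.

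The second stake is precision. With dropout near 60% and recruitment stopped for lack of patients (Sample size), precision available from data already collected is worth having.

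**Working it through.** **1. Can the two descriptions mean the same thing?** For a single baseline value, adjusting could be loose wording for subtracting. For items 6 and 19 it cannot: one subtraction does not remove two earlier values. The endpoint section therefore reads most naturally as regression adjustment, and the methods section as change.

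**2. Reproduce the SAP's own figure.** Inputs from the sample size section: reductions of 60.34 and 32.73 pp, so the difference is 60.34 − 32.73 = 27.61 pp; SD 34.5 pp; two-sided alpha 0.05; 29 per group.
- Noncentrality: 27.61 / (34.5 × √(2/29)) = 3.047, with 56 degrees of freedom.
- Exact t power: 0.850, as the SAP states. The original 34 per group gives 0.902, also as stated.
- 95% CI half-width: 2.003 × 34.5 × √(2/29) = 18.1 pp.

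The sample size thus rests on an unadjusted t test of the reduction, which is the change reading.

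**3. Compare ANCOVA.** The SAP gives no baseline SD and no correlation or slope. Assumptions: 34.5 pp is the SD of change, the baseline SD sB is 25 pp, and the slope b of follow-up on baseline takes a range of values. Then

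residual variance = 34.5² − (1 − b)² × sB²

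with 58 − 5 = 53 degrees of freedom (intercept, treatment, baseline, age group, sex).

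| Model | Residual variance | Residual SD (pp) | Power | Half-width (pp) |
|---|---|---|---|---|
| Change ANOVA | 1190.25 | 34.5 | 0.850 | 18.1 |
| ANCOVA, b = 0.3 | 1190.25 − 306.25 = 884.0 | 29.7 | 0.935 | 15.7 |
| ANCOVA, b = 0.5 | 1190.25 − 156.25 = 1034.0 | 32.2 | 0.894 | 16.9 |
| ANCOVA, b = 0.7 | 1190.25 − 56.25 = 1134.0 | 33.7 | 0.865 | 17.7 |
| ANCOVA, b = 1 | 1190.25 | 34.5 | 0.849 | 18.2 |

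At b = 0.5, baseline SDs of 15, 20, 25 and 30 pp give power 0.865, 0.878, 0.894 and 0.913. Any precision gained from age and sex themselves is not counted.

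**4. How far apart can the two estimates be?** They differ by (1 − b) times the chance baseline difference between arms. Without stratification that gap has an SD of (1 − b) × 25 × √(2/29): 4.6, 3.3 and 2.0 pp at b = 0.3, 0.5 and 0.7. Stratifying on baseline heavy drinking days makes it smaller.

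**5. Cost of two extra covariates.** Going from 55 to 53 degrees of freedom lowers ANCOVA power by 0.0003 to 0.0005 over these cases.

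**The case against.** **The methods section already settles it.** It is the only text naming the main model, it covers all continuous outcomes, and the sample size calculation agrees with it. This is a fair case for change ANOVA as the intended model. It still leaves the primary endpoint definition unreconciled, and it cannot carry out items 6 and 19 as written. The no-covariate sentence also says only that adjustment is unnecessary in principle, so it does not rule adjustment out.

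**The gain is small and rests on assumptions.** This stands in part. At slope 0.7 the half-width falls only from 18.1 to 17.7 pp, and at slope 1 not at all. The 25 pp baseline SD is an assumption. It should not be justified by an even spread over 5 to 30 heavy drinking days: that spread has a mean of 17.5/30 = 58.3%, too low to allow the 60.34 pp reduction used in the sample size calculation.

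**Age and sex.** Leaving out stratification factors does not invalidate the test; if anything it makes it conservative. Including them is good practice at almost no cost, and no separate harm has been quantified here.

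**Stronger readings that the SAP does not support.**
- A reader might infer bias or an underpowered trial. Randomisation keeps both estimators unbiased with complete data, and the unadjusted analysis is the one the trial was sized on.
- A reader might infer that baseline drinking is ignored. It enters the primary analysis either way, as a covariate or by subtraction.
- A reader might see a contradiction in the SPECT item, "from baseline SPECT-scan to follow-up after 26 weeks of treatment, adjusted for baseline". Change adjusted for baseline is ordinary ANCOVA and gives the same treatment estimate as ANCOVA of the follow-up value.

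**Conclusion.** The inconsistency is real and should be fixed. The primary endpoint and items 1 to 19 call for baseline adjustment, the named model is a change analysis without covariates, and no text reconciles them. The consequence is a primary p-value that depends on an unsettled choice, plus a possible loss of precision. If 34.5 pp is the SD of change and the baseline SD is 25 pp, choosing change ANOVA gives up between 0.4 pp (slope 0.7) and 2.4 pp (slope 0.3) of CI half-width at 29 per group. The same choice forgoes 0.015 to 0.085 in power. These sizes are illustrative, because the SAP supplies neither the baseline SD nor the slope. The contradiction itself rests on the text alone.

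**What to change.** In Analysis methods, replace the ANOVA sentence and the no-covariate sentence with:

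> The primary outcome is analysed by a linear model (ANCOVA) of the week-26 percentage of heavy drinking days on treatment, baseline percentage of heavy drinking days (continuous), age group as used in randomisation, and sex. Week 26 is the time point given under Primary endpoint, and missing values are handled as described under Missing data. Other continuous clinical outcomes (items 1 to 20) use the same model with their own baseline value.

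In addition:
- State the age cut used in randomisation.
- Use the same model in the multiple imputation analysis and in the imputation sensitivity analyses under Sensitivity analysis and Missing data. Show the unadjusted result alongside as supportive.
- **Item 19:** make the baseline-adjusted comparison the main one. Adjustment for the week-26 value, which is measured after randomisation, becomes supplementary. Fix this before the unblinded long-term analysis.
- **Item 6:** report the baseline-adjusted comparison and the stated baseline-plus-week-4 adjustment side by side. Note that week 4 is after randomisation, and that the Sensitivity analysis section itself questions the baseline SCIP because of chlordiazepoxide at screening.
- Leave the fMRI items 21 and 22 unchanged.

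The cost is SAP wording and two degrees of freedom, a power loss below 0.001. All covariates are already collected.

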# Withdrawal/Follow up

All patients who have withdrawn from the intervention and have been included for at least eight weeks (steady-state plasma level) were encouraged to participate in the last week 26 follow-up including brain scans at the time of withdrawal. If successful, individuals will be contacted for a long-term follow-up after further 26 weeks. All other individuals e.g individuals who withdraw before eight weeks and lost to follow-up will not be contacted for a long-term follow-up. Data will be presented in a Kaplan Meyer survival curve

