#### Sensitivity analysis

Sensitivity analysis is planned for the outcomes: heavy days, total alcohol intake, 0-days with the following assumptions:

- 1. We assume the drop-out is caused by a relapse in alcohol intake, and therefore we will impute the values of the missing final data for the above categories, as the baseline value and half a baselinevalue.
- 2. We assume the missing data are MNAR and will make a per protocol (PP) analysis.

We assume that the amount of chlordiazepoxide at screening will influence the baseline SCIP and PACS score. We will do a sensitivity analysis and compare the SCIP-results from week 4 with the baseline results, to see if there is a difference.

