# Missing data

Missing data will be imputed using the multiple imputation method. However, for multiple imputations to work properly we need to assume that the data are missing at random (MAR) which may not be the case in our study. Consequently, as a sensitivity analysis of handling the missing data, we will consider two realistic alternatives for the missing mechanism: 1) to assume that all non-observed individuals at 26 weeks have reverted to their pre-study drinking habit, and 2) that all non-observed individuals at 26 weeks have halved

**EXALT** study

Statistical Analysis Plan

Edition: 1.0

EudraCT 2016-003343-11

their drinking. If only multiple outcomes are missing then we will use a linear mixed-effect model which is an extension of the ANOVA model for analyzing the data.

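### The analysis section's last-observation endpoint conflicts with the week-26 alcohol endpoints and with the plan to impute patients not observed at week 26

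*SAP*

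**What the plan says.** The Analysis methods section states that all continuous outcomes, with alcohol use among the examples, "will be analyzed using ANOVA from baseline to last observation endpoint". It adds that covariate adjustment is in principle not needed because the trial is randomised.

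The endpoint sections name a fixed time and a baseline adjustment. The primary endpoint is "Percentage of heavy drinking days during the last 30 days, at follow-up after 26 weeks of treatment adjusted for baseline". Total alcohol intake is likewise taken "during the last 30 days, at follow up after 26 weeks of treatment adjusted for baseline", and alcohol-free days follow the same pattern.

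On missing values, the Missing data section says "Missing data will be imputed using the multiple imputation method". Because data may not be missing at random, it adds two scenarios: "all non-observed individuals at 26 weeks have reverted to their pre-study drinking habit", or have halved their drinking. The Sensitivity analysis section applies the same two assumptions to heavy drinking days, total intake and alcohol-free days, to "impute the values of the missing final data for the above categories", on the ground that dropout reflects relapse.

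Under Withdrawal/Follow up, patients who withdrew after at least eight weeks "were encouraged to participate in the last week 26 follow-up including brain scans at the time of withdrawal". Timing of outcome assessments gives a window of two weeks either side and records irregularities as protocol deviations. Recruitment reports that the last main-study visit was planned for 8 April 2020 but that all patients were terminated on 14 March 2020 because of COVID-19.

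**The concern.** The sections point to different observations for the same outcome. If the last available value is analysed, a patient with any post-baseline drinking record has an outcome and nothing is left to impute. If the week-26 value is analysed, the same patient is missing, goes into the multiple imputation and is covered by the return-to-baseline and half-baseline scenarios.

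With dropout near 60%, this choice may decide the analysed value for many patients. The scenarios are meant to test relapse-driven dropout. They could leave out part of the group they target, because those patients would count as observed on the strength of an early assessment. Two analysts following the SAP could reach different primary and sensitivity results.

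**Working it through.** **Inputs.** Dropout nearly 60% (Sample size); planning reductions of 60.34 and 32.73 percentage points (pp), SD 34.5 (Justification of sample size); 30-day look-back (Primary endpoint); withdrawal assessment from week 8 (Withdrawal/Follow up); window of two weeks either side, with visits performed one week late, so week 27 (Timing of outcome assessments); visits at weeks 4, 12, 20 and 26 (Trial design).

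**The plan's own figure.** Difference = 60.34 − 32.73 = 27.61 pp. A two-sided t test at 5% with SD 34.5 and 29 per group has power 0.850, as stated. 58/0.40 = 145, against 144 stated, a rounding difference. The sample size is not affected by this point; the check only confirms the inputs.

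**Which value is analysed for a patient who withdraws at week 10 and is assessed then?**
- Analysis methods, read literally: the week-10 value.
- Primary and Secondary endpoints: the week-26 value, which does not exist.
- Missing data: imputed, if the patient counts as not observed at 26 weeks.
- Withdrawal/Follow up: the assessment carries the week-26 label.
- Timing of outcome assessments: outside the window and a protocol deviation, with no statement on whether the value is used.

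No section decides between these.

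**How different is an early value? (illustration)** The look-back is 30/7 = 4.29 weeks.
- Endpoint period: 26 − 4.29 = 21.71, so about weeks 21.7 to 26.
- Week-8 assessment: 8 − 4.29 = 3.71, so about weeks 3.7 to 8.
- Share of weeks 8 to 26 with no overlap: (21.71 − 8)/18 = 76%. Share before the window opens at week 24: (24 − 8)/18 = 89%. Centred on week 27, the shares are (22.71 − 8)/19 = 77% and (25 − 8)/19 = 89%. These are shares of time, not of patients.
- Week 20 is 42 days before week 26, so it does not overlap either. The SAP does not say whether drinking was recorded at that visit.

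**Administrative terminations.** 14 March to 8 April 2020 is 25 days, or 3.6 weeks. If the 8 April visit was due at week 26 or 27, that patient was at about week 22.4 or 23.4, before the window opens at week 24 or 25. The SAP gives neither the number of such patients nor whether they were assessed.

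**Return-to-baseline scenario (illustration).** Assume 60% dropout in each arm and the planning reductions in completers. Let f be the share of dropouts counted as observed from an early assessment and k their reduction relative to completers; neither is in the SAP. Then:

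difference = 27.61 × (0.40 + 0.60 × f × k)

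| f | patients reached by the scenario, 60% × (1 − f) | k = 0 | k = 0.5 | k = 1 |
|---|---|---|---|---|
| 0 | 60% | 11.0 pp | 11.0 pp | 11.0 pp |
| 0.25 | 45% | 11.0 pp | 13.1 pp | 15.2 pp |
| 0.50 | 30% | 11.0 pp | 15.2 pp | 19.3 pp |
| 0.75 | 15% | 11.0 pp | 17.3 pp | 23.5 pp |

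The rule makes no difference if early values show no reduction, and a large one if they show the full reduction.

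**The case against.** The analysis sentence is generic, while the endpoints are defined item by item at week 26, and specific text can be held to govern general text. The SAP never names carry-forward, and its imputation plan would have little to do if carry-forward were meant. This is fair: a reader might infer that the trial plans last-observation-carried-forward, and the SAP does not establish that. It does contain a sentence that permits it, naming alcohol use, in the section an analyst follows.

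There is also support for treating the withdrawal assessment as the final value. The SAP gives it the week-26 label, counts the long-term follow-up from it, and describes scans as repeated when patients finished the study. The window text excludes no data. So a reader who infers that the SAP is silent on these assessments, or that it treats them as missing, goes too far. But these passages describe a visit and its content. They are not an analysis rule, and they sit beside imputation for patients not observed at 26 weeks.

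A reader might also take 15.2 to 23.5 pp as the expected distortion. That is not supported: f and k have no source in the SAP, the range concerns one sensitivity scenario, and the effect on the primary analysis is not quantified.

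Finally, declaring every off-window value missing for every outcome would overreach. It would discard the brain scans deliberately collected at withdrawal. It would also put any COVID-19 terminations assessed early into a scenario justified by relapse, which is not why those patients stopped.

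**Conclusion.** The contradiction stands for the alcohol outcomes and should be corrected. The analysis section sets one time point, while the endpoint and missing-data sections require another. The withdrawal assessments, the March 2020 terminations and the lack of a rule for off-window values turn loose wording into a real choice for the analyst.

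Nearly 60% dropout is an upper guide to how many patients the choice could touch. At the two planned sizes of 114 and 144 this is about 68 and 86 patients (0.60 × N). The affected share is smaller to an unknown degree, since patients who withdrew before week 8 or were lost to follow-up were not offered the withdrawal assessment. The size and direction of any bias cannot be derived from the SAP; the time shares and the table show only that the choice can matter. Confidence is high that the texts conflict and moderate about the consequence.

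**What to change.** - In Analysis methods, for heavy drinking days, total intake and alcohol-free days, replace the last-observation phrase with: *the week-26 value, adjusted for baseline; if missing, multiple imputation as described under Missing data*. Bring the remark on covariate adjustment into line, since the endpoints call for baseline adjustment. State whether the two-week window is centred on week 26 or week 27.
- For these outcomes, keep withdrawal values from before the window at their actual study week, as input to the imputation. Include these patients in the baseline and half-baseline scenarios.
- Report a supportive analysis that counts the withdrawal assessment as the final value, because the SAP's own description gives that reading some support.
- State separately how patients terminated on 14 March 2020 are handled. The relapse rationale does not cover them.
- Keep brain scans taken at withdrawal as the follow-up session in the imaging analyses.

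The change is to wording only, provided it is made before participants are divided into groups A and B. The price is fewer observed week-26 values and a somewhat wider confidence interval. In the return-to-baseline and half-baseline scenarios, some recorded post-baseline drinking gives way to an assumed value. That is a defensible choice but not the only one, and the supportive analysis shows how much depends on it.
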